5.6.1 Premature termination of the study

If the investigator, AstraZeneca, or the Medical Monitor becomes aware of conditions or events that suggest a possible hazard to patients if the study continues, the study (or part of the study) may be terminated after appropriate consultation between the relevant parties. The study may also be terminated early at the Sponsor's discretion in the absence of such a finding.

Conditions that may warrant termination include, but are not limited to:

- Decision of the SMC (see Section [6.6](#))
- The discovery of an unexpected, significant, or unacceptable risk to the patients enrolled in the study
- Failure to enrol patients at an acceptable rate
- A decision on the part of AstraZeneca to suspend or discontinue development of AZD8931.

5.7 Data management

5.7.1 Case report forms

pCRFs will be used to record all data except for results of blood sample evaluations collected by the central laboratory. Raw laboratory and PK data will be electronically transferred to Data Management for inclusion in the study database. The transfer of derived data will be described in the statistical analysis plan (SAP).

Data should be recorded legibly in English onto the pCRFs in black ballpoint pen. Corrections should be made legibly and initialled and dated by approved personnel; the reasons for significant changes must be provided. Correction fluid or covering labels must not be used.

The study monitor will check data at the monitoring visits to the study site. The investigator will ensure that the data in the pCRFs are accurate, complete and legible.

pCRFs will be printed in at least triplicate on carbonless paper. The white copy of the pCRFs will be sent to Data Management, the green copy will be retained by the investigator in the site files, and the pink copy will be retained in the monitor's file.

Data from the completed pCRFs will be entered onto the study database by Data Management using double-data entry, and validated under the direction of the Data Manager. Any missing, invalid or inconsistent recordings in the pCRFs will be referred back to the investigator using a data query form and be documented for each individual patient before clean file status is declared.

The patient diary is primarily used to assess patient dosing compliance. Data from the patient diary will only be transcribed into the pCRF if appropriate. Any text must be translated into English before transcribing.

5.7.2 Genetic data

In the case of genotyping data, only the date and time the patient gave consent to participation in the genetic research and the date the blood sample was taken from the patient will be recorded in the pCRF and database.

The genotyping data generated from the study will be stored in the AstraZeneca Laboratory Information Management System (LIMS) database or other appropriate system. This database is a secure database, which is separate from the database used for the main study. Some or all of the datasets from the main study may be duplicated within the AstraZeneca LIMS database for exploratory genetic analysis.

However, some or all of the clinical study dataset may be duplicated within the AstraZeneca LIMS database or other appropriate system for exploratory analysis.

5.8 Reporting of genotyping results

See [Appendix G](#).

6. PHARMACOKINETIC, PHARMACODYNAMIC, SAFETY, GENETIC AND STATISTICAL METHODOLOGY

6.1 Pharmacokinetic / pharmacodynamic evaluation

6.1.1 Calculation or derivation of pharmacokinetic variables

The PK analyses will be performed by Clinical Pharmacology and DMPK AstraZeneca.

PK parameters to be calculated are:-

- Single dose plasma PK
 - AUC from time zero to 12 hours (AUC_{0-12}), 24 hours (AUC_{0-24}), time t (AUC_{0-t}) and infinity (AUC) after dosing, C_{max} , t_{max} , $t_{1/2}$, total apparent drug clearance (CL/F), apparent volume of distribution at (V/F)
- Multiple dose plasma PK
 - time to ss and assessment of any accumulation of AZD8931, including AUC_{SS0-12} , C_{SSmax} , time to reach maximum plasma concentration at steady state (t_{SSmax}), CL_{SS}/F , C_{SSmin} , accumulation ratio (R_{AC}) and linearity factor

Other PK parameters may be determined if deemed appropriate.

Minimum plasma concentration (C_{min}), C_{max} and t_{max} (and C_{SSmin} , C_{SSmax} and t_{SSmax}) will be determined by visual inspection of the plasma concentration time profile. The area under the plasma concentration time curve from time zero to 12 and 24 hours after dosing, AUC_{0-12} and AUC_{0-24} , respectively, and from zero to the time of the last quantifiable plasma concentration, AUC_{0-t} , will be calculated using the linear trapezoidal rule (linear/log interpolation). The $t_{1/2}$ will be calculated from the equation $\ln(2)/\lambda_z$ (where the rate constant of the slowest disposition phase [λ_z] will be calculated by log linear regression of the terminal portion of the concentration time profile where there are sufficient data [ie, the terminal phase is followed for at least $3 \times t_{1/2}$]). The AUC will be derived by using λ_z to extrapolate AUC_{0-t} to infinity. CL/F and V_{SS}/F will be estimated by dividing the dose by the AUC and multiplying mean residence time by CL/F, respectively. Linearity factor will be determined by dividing AUC_{SS0-12} by AUC after the single dose and R_{AC} will be determined by dividing AUC_{SS0-12} by AUC_{0-12} after the single dose.

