The non-validated PK results showed that AZD8931 is orally bioavailable over the dose range 2.5 mg to 200 mg. Absorption was moderately rapid with time to reach maximum plasma concentration (t_{max}) occurring in most subjects at 1.5 or 2 hours after the dose (range 0.5 to 4 hours). After reaching the maximum plasma concentration (C_{max}), plasma concentrations declined biphasically. A terminal phase became apparent from about 24 hours after the dose,

when the plasma concentrations had fallen to around 6% of the peak values. The mean terminal elimination half-life ($t_{1/2}$) across the dose range was 12.1 hours (range 7.6 to 16.6 hours).

Based on the above data, it was determined that twice-daily administration should be employed in the current study to avoid excessive fluctuations between steady state (ss) C_{max} ($C_{ss_{max}}$) and minimum plasma concentration ($C_{ss_{min}}$). It is predicted that twice-daily dosing will lead to accumulation of study drug at about 30%, with a 5-fold fluctuation between $C_{ss_{min}}$ and $C_{ss_{max}}$.

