4.2.2 Collection of biological samples

PK samples will be collected at the following time points for determination of AZD8931 plasma concentrations:

Days D1 and R14: pre-dose, 1, 2, 4, 6, 8, 12 (prior to AZD8931 administration on Day R14), 24 (D1 only), 48 (D1 only) and 72 (D1 only) hours post dose Days R3 and R7: pre-dose (see [Table 1](#)).

Depending on emerging data/information, the timings and number of PK samples may be altered, but the maximum blood volumes from scheduled samples given in [Table 3](#) will not be exceeded. The actual sample time and date of all PK samples must be recorded in the CRF.

All biological samples will be collected, processed, labelled and shipped to a central laboratory (), as per the laboratory study manual. At appropriate time intervals, the central holding laboratory will arrange to have the samples transported on dry ice to the appropriate laboratory(ies) for analysis. Samples should be analysed within the timeframe after collection for which the stability in the samples has been validated and found acceptable.

Samples will be disposed of after the Clinical Study Report has been finalised.

Venous blood samples (3 mL) for determination of AZD8931 in plasma will be taken at the timepoints detailed in the study plan (see [Table 1](#)).

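### The three-half-life rule for the terminal rate constant conflicts with sampling that stops at 72 h: half-lives above about 16 h drop out because they are long

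*Protocol*

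**What the plan says.** Section 6.1.1 estimates the terminal rate constant by log-linear regression only "where there are sufficient data [ie, the terminal phase is followed for at least" three half-lives. It gives no rule for profiles that fall short.

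The dependent parameters are defined in the same paragraph:
- "The AUC will be derived by using λ_z to extrapolate" the measured area to infinity.
- CL/F and Vss/F come from "dividing the dose by the AUC and multiplying mean residence time by CL/F, respectively".
- "Linearity factor will be determined by dividing" the steady-state 12-hour AUC by the single-dose AUC.

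Section 4.2.2 sets the late single-dose samples at "24 (D1 only), 48 (D1 only) and 72 (D1 only) hours post dose". Section 1.1.2 describes the healthy-volunteer data: "A terminal phase became apparent from about 24 hours after the dose", at around 6% of peak, and the mean half-life "across the dose range was 12.1 hours (range 7.6 to 16.6 hours").

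On volume, the parameter lists in the synopsis and section 6.1.1 show V/F, while the calculation text in section 6.1.1 produces Vss/F.

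**The concern.** A completeness rule expressed in multiples of the quantity being estimated is harder to meet the larger that quantity is. If the sampling window is short relative to plausible half-lives, values go missing because they are large, and the summary of what remains is biased low. The documents' own figures put the cut-off inside the range already seen in volunteers.

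Single-dose PK is a secondary objective (section 2.2) and cohorts hold 3 to 6 patients, so one selective loss is a visible share of a dose level's data. The linearity factor, which compares steady-state with single-dose exposure, is lost for the same patients.

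**Working it through.** **Schedule check.** Day 1 has 10 samples (pre-dose, 1, 2, 4, 6, 8, 12, 24, 48, 72 h), Day R14 has 7, and R3 and R7 have one each: 10 + 7 + 1 + 1 = 19, and 19 × 3 mL = 57 mL. This reproduces Table 3, so 72 h is the last single-dose sample.

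**Longest qualifying half-life** = (last sample − start of terminal phase)/3.

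| Start of terminal phase | Last usable sample | Limit |
|---|---|---|
| 24 h (section 1.1.2) | 72 h | 48/3 = 16.0 h |
| 18 h (assumed) | 72 h | 54/3 = 18.0 h |
| 12 h (assumed) | 72 h | 60/3 = 20.0 h |
| 24 h | 48 h (72 h missing or unquantifiable) | 24/3 = 8.0 h |

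At 16.6 h the rule needs 3 × 16.6 = 49.8 h of terminal phase, that is sampling to 73.8 h; the window covers 48/16.6 = 2.89 half-lives. At the mean of 12.1 h it needs 36.3 h, to 60.3 h, so such a patient passes only if the 72 h sample is usable.

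**Share affected.** Assume normal half-lives with mean 12.1 h. The protocol gives no SD; the range width is 16.6 − 7.6 = 9.0 h, and one quarter to one third of it gives 2.25 to 3.0 h.

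| Quantity | SD 2.25 h | SD 3.0 h |
|---|---|---|
| z = (16 − 12.1)/SD | 1.73 | 1.30 |
| p = P(half-life > 16 h) | 0.042 | 0.097 |
| At least one lost of 3: 1 − (1 − p)³ | 12% | 26% |
| At least one lost of 6: 1 − (1 − p)⁶ | 22% | 46% |
| Mean of those kept: 12.1 − SD·φ(z)/Φ(z) | 11.9 h | 11.5 h |

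**Is the exclusion needed to protect AUC?** Take 6% of peak at 24 h and let all of it decline at the terminal rate. In units of peak × hours:
- Area beyond 72 h = 0.06 × 2^(−48/t½) × t½/ln 2. This is 0.19 at 16.6 h and 0.52 at 24 h.
- Rough total area = 1.0 (linear rise to a peak at 2 h) + 7.35 (log-linear fall from peak to 6% over 22 h: 0.94 × 22/ln(1/0.06)) + the tail from 24 h, 0.06 × t½/ln 2 (1.44 or 2.08). This is 9.8 or 10.4.
- Fraction beyond 72 h: 0.19/9.8 = 2% at 16.6 h and 0.52/10.4 = 5% at 24 h.

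Two-phase oral profiles fitted to the protocol's figures give 0.6 to 1.9% and 2.1 to 4.7%. Halving the 2 to 24 h area, to allow for a steeper early fall, gives 0.19/6.1 = 3% and 0.52/6.8 = 8%. All are small.

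**Volume.** Mean residence time after an oral dose includes absorption time. Fitted profiles give an absorption time of about 1.06 h against a disposition residence time of about 7.94 h, an overstatement of 1.06/7.94 = 13%; other fits give down to 8%.

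**The case against.** The strongest reply is that 24 h is an approximate onset from non-validated volunteer data, so 16 h is not a hard ceiling. That stands: an onset at 12 h would lift the limit to 20 h, above the observed range. But 24 h is the only figure the protocol offers, and an unusable 72 h sample moves the limit much further the other way.

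A reader might infer that the patients with the highest exposure vanish and that escalation decisions are misled, because section 3.2.1 ties corneal toxicity to cumulative AUC and section 3.1.2 lets exposure slow escalation. The documents do not support this. AUC0-12, AUC0-24, AUC0-t, the steady-state 12-hour AUC, CLss/F and the accumulation ratio need no terminal rate constant, so the SMC still sees exposure. A long terminal half-life is also not the same as high exposure when that phase starts at about 6% of peak. Bias in AUC or CL/F follows only so far as slow elimination reflects low clearance.

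A wider spread would enlarge the problem: an SD of 4 h gives 17% failing and 66% of six-patient cohorts affected. That SD fits poorly with a 9.0 h range across six dose levels.

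Section 4.2.2 allows sample times to change, but commits to nothing. Nor is this merely analysis-plan detail: section 6.1.1 itself fixes the rule.

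**Conclusion.** The conflict holds on the protocol's figures: the rule and schedule together admit half-lives up to about 16 h, and 16.6 h has been seen. The half-life summary is biased low by about 0.2 to 0.6 h (12.1 h to 11.9 or 11.5 h), with 4 to 10% of patients losing half-life, AUC to infinity, CL/F, Vss/F and linearity factor. This rests on four assumptions: onset near 24 h; a usable 72 h sample; normal half-lives with SD 2.25 to 3 h; and patients eliminating the drug as volunteers did. If patient half-lives were 20% longer, with mean and SD both scaled, the share failing would be about 29 to 34%.

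The affected variables are secondary and descriptive, and the DLT and MTD rules do not depend on them. The point is of moderate weight: an avoidable, value-dependent loss in small cohorts.

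The volume point is minor: the listed and calculated parameters differ, and the formula carries absorption time.

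**What to change.** In section 6.1.1, replace the exclusion with two statements:
- Report the half-life and flag it when the terminal phase was followed for fewer than three half-lives; summarise with and without flagged values.
- Retain AUC to infinity, CL/F and linearity factor whenever the extrapolated fraction is below a prespecified limit. A limit of 20% is an example, not a figure from the protocol; the fractions above lie well inside it.

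Do not trade the rule for one that requires the 24, 48 and 72 h samples all to be quantifiable. At a 7.6 h half-life the 72 h level is about 6% × 2^(−48/7.6) = 0.08% of peak, so fast eliminators could then be the ones lost.

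On volume, make label and formula agree and state that oral mean residence time includes absorption. If dose/(terminal rate constant × AUC) is used, label it Vz/F. It does not substitute for Vss/F: at 12.1 h it equals CL/F × 12.1/ln 2 = CL/F × 17.5 h, about 2.2 times the value from a disposition residence time of about 8 h.

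The cost is a few sentences and some flagged half-lives of lower precision. No change to visits or sampling is needed.

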- If DLT is observed in ≥ 2 patients within the DLT evaluation period then this dose will be declared as non-tolerated and dose escalation will stop. A lower dose may be investigated at the discretion of the SMC (Section 6.6).
- If during the DLT evaluation period a DLT is observed in 1 patient within a dose level cohort consisting of less than 6 evaluable patients, additional patients will be recruited, to maintain a maximum of 6 evaluable patients in the cohort
- If during the DLT evaluation period there are no DLTs observed within a dose level cohort, containing 3 to 6 patients evaluable for the presence of DLT, then the dose will be defined as tolerable and dose escalation will continue with an incremented increase in a new group of at 3-6 patients.

Figure 1 summarises the rules to be applied.

Figure 1 Phase I dose escalation decision tree

Footnotes:

Patients in the above schematic refer to evaluable patients (dose escalation set).

^a At the discretion of the SMC, in order to explore any safety concerns in the absence of DLT, each dose level cohort may be expanded to include a maximum of 6 patients who are evaluable for the dose escalation set.

Abbreviations: DLT: dose-limiting toxicity, MTD: maximum tolerated dose

The dose will initially be escalated by dose doubling, up to a level where the SMC decide that smaller escalation steps are warranted, based on PK and/or safety data. If the exposure in patients is more than 10% to 15% greater than predicted based on data obtained in healthy subjects, the dose escalation may proceed in a more conservative manner. The SMC will determine the dose escalation based on the above criteria at the end of each dose group.

Based on emerging data, including PK and/or safety data and/or pre-clinical data, the SMC can consider alternative schedules, including once-daily dosing of AZD8931, in consultation with AstraZeneca and

When a non-tolerated dose is defined, dose escalation will be stopped and the MTD will be confirmed (see Section 3.1.4).

Following each dose decision, the patients already receiving study medication may remain on treatment at their original dose if, in the opinion of the investigator, the patient is receiving some benefit from therapy, is free from intolerable toxicity and does not meet one of the discontinuation criterion listed in Section 3.3.5.1.

Intra-patient dose escalation is not permitted.

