4.6 Volume of blood sampling

The total volume of blood that will be drawn from each patient in this study is as follows:

Table 3 Volume of blood to be drawn from each patient

Assessment	Sample volume (mL)	Number of samples per patient	Total volume per patient (mL)
Pharmacokinetics	3.0	19	57.0
Safety ^a	c		144.0 ^d
Pharmacogenetics ^b	9.0	1	9.0
Cell death (proapoptotic) biomarkers ^b	3.0	6	18.0
Total (with optional samples)			228 ^d
Total (without optional samples)			201 ^d

INR = International Normalized Ratio

- a Including clinical chemistry and haematology (11 samples each per patient), glucose and potassium (6 hours post-dose on days D1 and R14) (2 samples per patient), and screening tests (INR etc.).
- b Optional sample.
- c Safety laboratory assessments will be performed locally at each centre's laboratory by means of their established methods. The blood volumes are therefore subject to site-specific change.
- d Approximate maximum volume.

For patients who continue dosing beyond the DLT evaluation period, a blood sample for laboratory safety analyses and an optional blood sample (3 mL) for proapoptotic biomarkers may be collected at each visit.

Extra blood samples may also be collected if, for example, additional samples are required for repeat safety assessments or additional PK assessment, but will be not greater than 10% more of the planned volume.

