- Stop escalation and investigate lower dose(s) – the lower dose may be intermediate between the previous dose level and current dose level
- End study.

A consensus decision must be made. The SMC may seek advice from further experts, including qualified representatives of AstraZeneca, in order to reach a consensus decision. All decisions will be documented, and distributed to all SMC members.

No formal statistical analyses will be performed in the safety review.

Based on emerging data, including PK and/or safety data and/or pre-clinical data, the SMC can consider alternative schedules, including once-daily dosing, in consultation with AstraZeneca and

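### The linearity factor in Section 6.1.1 is tied to a 12 h steady-state AUC and would read about 0.8 instead of 1 in any once-daily cohort

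*Protocol*

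**What the plan says.** Section 6.1.1 lists the multiple-dose parameters and names a single steady-state AUC, over 0-12 h. It then sets two ratios on it:

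- Linearity factor: "Linearity factor will be determined by dividing AUC_{SS0-12} by AUC after the single dose".
- Accumulation ratio: "R_{AC} will be determined by dividing AUC_{SS0-12} by AUC_{0-12} after the single dose".

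For clearance, only the single-dose calculation is given: "CL/F and V_{SS}/F will be estimated by dividing the dose by the AUC". CLss/F appears in the parameter list without a formula.

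Dosing is planned as twice daily, but Section 3.1.2 states that "the SMC can consider alternative schedules, including once-daily dosing of AZD8931". The synopsis and Sections 3.1.1, 3.2.1 and 6.6 carry the same option.

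Section 4.2.2 schedules a full profile to 12 h on Days D1 and R14, with later samples at "24 (D1 only), 48 (D1 only) and 72 (D1 only) hours post dose". The same section adds: "Depending on emerging data/information, the timings and number of PK samples may be altered", subject to the Table 3 volumes for scheduled samples. Section 4.6 allows extra samples, including for additional PK assessment, "but will be not greater than 10% more of the planned volume".

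**The concern.** For a drug with linear, time-invariant kinetics, the AUC over one full dosing interval at steady state equals the single-dose AUC to infinity. A linearity factor built on that identity should be 1, and a departure from 1 is read as time-dependent kinetics. The identity needs the whole interval. With once-daily dosing the interval is 24 h, so an AUC cut at 12 h falls short of the single-dose AUC even when nothing non-linear is happening.

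Multiple-dose PK is a secondary objective (Section 2.2), PK endpoints are summarised by dose level (Section 6.4.4.1), and PK is one of the grounds on which the SMC may change the schedule. A once-daily cohort would appear to have lower steady-state exposure than its single dose predicts, and its linearity factor could not be set beside those of the twice-daily cohorts.

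**Working it through.** **Inputs from the protocol**

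- Section 1.1.2 (healthy volunteers): predicted accumulation on twice-daily dosing about 30%; concentration about 6% of peak at around 24 h; peak mostly at 1.5 or 2 h; mean terminal half-life 12.1 h (range 7.6 to 16.6 h).
- Section 4.2.2: D1 samples pre-dose, 1, 2, 4, 6, 8, 12, 24, 48 and 72 h (10); R14 samples pre-dose, 1, 2, 4, 6, 8 and 12 h (7); one pre-dose sample each on R3 and R7.

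**Reproducing the plan's own count.** 10 + 7 + 1 + 1 = 19 samples, and 19 × 3 mL = 57 mL, which agrees with Table 3. The scheduled R14 profile therefore ends at 12 h.

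**Assumptions.** Linear kinetics; each repeat dose equals the D1 single dose; the 30% is read as the AUC ratio that Section 6.1.1 calls R_AC.

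**Twice daily.** AUCss0-12 = AUC, so the linearity factor is 1.00 and the stated formula is right. Also R_AC = AUCss0-12/AUC0-12 = AUC/AUC0-12 = 1.30, so AUC0-12/AUC = 1/1.30 = 0.77. The remaining 0.23 of the single-dose AUC lies after 12 h.

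**Once daily, formula as written.** By superposition, AUCss0-12 is the sum of the single-dose areas over 0-12, 24-36, 48-60 h and so on.

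- Lower bound: the first area alone gives 0.77.
- Upper bound: concentrations fall after 12 h, so the area over 24-36 h is no larger than that over 12-24 h, the area over 48-60 h no larger than that over 36-48 h, and so on. At most half of the remaining 0.23 can be added: 0.77 + 0.115 = 0.885.

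The factor therefore lies between about 0.77 and 0.885 when it should be 1.00. No compartmental model is needed.

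**Cross-checks with models**

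- One-compartment decline through 6% of peak at 24 h, with the peak at 2 h: k = ln(1/0.06)/22 = 0.128 per h. Twice-daily accumulation is 1/(1 − e^(−12k)) = 1.28, close to the stated 30%. The once-daily factor is 1/(1 + e^(−12k)) = 0.82.
- Six illustrative biexponential oral profiles (terminal half-life 12.1 h, peak at 1.6 to 1.9 h, 6% to 9% of peak at 24 h, twice-daily accumulation 33% to 47%): once-daily factor 0.78 to 0.81 on 0-12 h and 1.00 on 0-24 h.
- If the terminal half-life governed the whole decline, the factor would be 0.67 (0.62 to 0.75). That implies twice-daily accumulation of about 2.0-fold (1.5 to 2.5), which conflicts with the protocol's 30%, so I do not rely on it.

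**CLss/F, only if it were dose/AUCss0-12.** The overstatement would be 1/0.885 = 1.13 to 1/0.77 = 1.30, that is 13% to 30%.

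**R_AC.** In the same biexponential profiles on once-daily dosing it is 1.08 to 1.15 on 0-12 h and 1.09 to 1.17 on 0-24 h, so it hardly changes.

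**After the change.** With the R14 pre-dose value used as the 24 h point and the scheduled R14 times, a linear/log trapezoidal calculation gives a factor of 0.99 in these profiles. An added 24 h sample instead would make 20 × 3 = 60 mL, against 57 × 1.10 = 62.7 mL.

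**The case against.** The strongest reply is that Section 6.1.1 describes the planned regimen. Dosing is twice daily, the objective on maximum tolerated dose is framed for twice-daily administration, and for that regimen the formula is correct. Once-daily dosing is something that the SMC may consider, and it may never happen. Section 6.1.1 also allows further PK parameters, so a 0-24 h AUC and a ratio built on it could be reported, and the label 0-12 shows the reader which interval was used. All of this limits the weight of the point. It does not remove it: freedom to add parameters or move samples does not redefine the linearity factor, and even with a 24 h sample on R14 the stated rule would still divide the 0-12 h area.

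A reader might infer more than the protocol supports:

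- **That R14 sampling is locked at 12 h.** It is not. Section 4.2.2 lets times and number change, Section 4.6 allows some extra volume, and at steady state the scheduled R14 pre-dose sample already gives the 24 h value.
- **That the plan prescribes a wrong CLss/F.** It prescribes none. Dose/AUC is stated for single-dose CL/F only.
- **That the accumulation ratio fails too.** It compares matching windows and is nearly unaffected.
- **That a change of schedule would bypass an amendment.** The protocol does not say so; Section 5.4 sets out the amendment route, and a revision could correct the formula at that time.
- **That escalation decisions would be misled.** No rule makes the linearity factor an escalation criterion; the decision rules in Section 3.1.2 rest on DLT counts.

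**Conclusion.** The point holds in a narrow form. Section 6.1.1 states the linearity factor without condition, and that rule is wrong for a schedule that the protocol itself leaves open. For a perfectly linear drug it would show a false shortfall of about 12% to 23% (a factor of 0.885 to 0.77) in a once-daily cohort. The size rests on reading the predicted 30% accumulation as an AUC ratio and on volunteer kinetics carrying over to patients. The direction does not depend on those figures, because half the dosing interval is left out. Any error in CLss/F is conditional on a formula that the plan does not state. Severity is low: the schedule is optional, the parameter is secondary and descriptive with no hypothesis attached, the twice-daily cohorts are correct, and the scheduled samples allow the correct value to be recovered at analysis.

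**What to change.** In Section 6.1.1, define AUCss, the linearity factor and CLss/F over the actual dosing interval τ: 0-12 h for twice-daily cohorts and 0-24 h for once-daily cohorts. The linearity factor becomes AUCss0-τ divided by single-dose AUC, and CLss/F becomes dose divided by AUCss0-τ. R_AC can stay as it is.

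In Section 4.2.2, state how the 12-24 h portion on R14 is obtained in any once-daily cohort, by one of two routes:

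- Use the scheduled R14 pre-dose concentration as the 24 h value. This assumes steady state by R14 and needs no extra blood.
- Take a 24 h sample before the next dose. This adds one 3 mL sample, giving 60 mL for PK. That exceeds the 57 mL in Table 3, so it would have to rest on the 10% allowance in Section 4.6 (62.7 mL on the PK volume).

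The cost is a few lines of wording. Nothing changes for the twice-daily cohorts.
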